## 7.1 Source Data Documentation

Source documents for the study:

- Electronic health records- Trakcare and SCI Diabetes
- Participant case report forms
- Study questionnaires
- Dexcom G6 glucose data on Dexcom Clarity
- Tandem pump and control IQ data on t:connect
- Food diary
- Ketone recording sheet

## 7.2 Case Report Forms

Participant data will be collected on paper case report forms. The case report form will be identified using the participant's unique study identifier and not identifiable information such as name or CHI. The case report form will be stored in locked and secure rooms in the ERICR /ERI outpatient department. Any electronic information collected will be stored on an NHS computer with password-controlled access. All patient identifiers will be removed and allocated a study ID number. This will be stored on a secure NHS server for 6 years.

# 8 DATA MANAGEMENT

## 8.1 Personal Data

The following personal data will be collected as part of the research:

- Name
- Address
- Date of birth
- Contact telephone number(s)
- Email address
- CHI number

Personal data will be stored by the research team in the Edinburgh Royal Infirmary under lock and key. Data will only be accessible by study staff. The code break will be kept on a password protected NHS computer.

Personal data will be stored for 12-24 months.

## 8.2 Data Information Flow

Data collected by study staff will be held on secure password protected NHS computers in the Edinburgh Royal Infirmary and in a locked cupboard in the Edinburgh Royal Infirmary. Only study staff will have access to this data. Anonymised reports on the study will be sent during the trial period to the Helmsley Charitable Trust, Tandem and Dexcom. The headquarters of these companies are based in the United States.

## 8.3 Transfer of Data

Data collected or generated by the study (including personal data) will not be transferred to any external individuals or organisations outside of the Sponsoring organisation(s).

Reports containing anonymised data will be sent during the trial period to the Helmsley Charitable Trust, Tandem and Dexcom.

## 8.4 Data Controller

A data controller is an organisation that determines the purposes for which, and the manner in which, any personal data are processed.

The University of Edinburgh and NHS Lothian are joint data controllers along with any other entities involved in delivering the study that may be a data controller in accordance with applicable laws (e.g. the site).

## 8.5 Data Breaches

Any data breaches will be reported to the University of Edinburgh and NHS Lothian Data Protection Officers who will onward report to the relevant authority according to the appropriate timelines if required.

# 9 STATISTICS AND DATA ANALYSIS

## 9.1 SAMPLE SIZE CALCULATION

Sample size is based on previous work by Cranston et al 'Restoration of hypoglycaemic awareness in patients with long-duration insulin dependent diabetes' which was published in the Lancet in 1994. They used a similar sample size in this study.

## 9.2 PROPOSED ANALYSES

In primary analyses, the glucagon response to insulin induced hypoglycaemia at 0 and 8 months will be compared to the individual's baseline glucagon responses within each group. In further exploratory analyses, the participants in the highest tertile of glycaemic TIR as a group over the 8 months will be compared to those in the lowest tertile over the 8 months as a

group. The rate of appearance (Ra) of the stable isotopes will be used as a marker of endogenous glucose production. Analysis of tracee:tracer ratio will be made by mass spectrometry. The TIR of participants completing the study 3-month extensions will be compared to that of group 2 during the study.

We predict minimizing exposure of alpha cells to hyperglycemia with AID +/- VLCD should significantly enhance glucagon.

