12.2.6	Confidentiality .....	43
12.2.7	Data Protection .....	43
13	STUDY CONDUCT RESPONSIBILITIES .....	44
13.1	PROTOCOL AMENDMENTS .....	44
13.2	MANAGEMENT OF PROTOCOL NON COMPLIANCE .....	44
13.3	SERIOUS BREACH REQUIREMENTS .....	44
13.4	STUDY RECORD RETENTION .....	44
13.5	END OF STUDY .....	44
13.6	CONTINUATION OF TREATMENT FOLLOWING THE END OF STUDY .....	45
13.7	INSURANCE AND INDEMNITY .....	45
14	REPORTING, PUBLICATIONS AND NOTIFICATION OF RESULTS .....	45
14.1	AUTHORSHIP POLICY .....	45
15	REFERENCES .....	46

Title	
Hypoglycaemia	
Precis	A pilot study of 8 months at home, closed loop + low carbohydrate diet (LCD) vs control.
Device	Tandem t:slim X2 with Control IQ and Dexcom G6 system.
Objectives	This study aims to look at the glucagon response to hypoglycaemia in 24 participants with T1D to ascertain if maximising time in range improves glucagon response to insulin-induced hypoglycaemia.
Study Design	Randomised clinical feasibility trial with a 1:1 randomisation to Control IQ + LCD and routine care. 3-month study extension phase for routine care group where they are converted to Control IQ technology.
End Point	To assess if maximising TIR can restore glucagon secretions in T1D.
Population	Adults with c-peptide negative T1D
Sample Size	24 participants
Treatment Groups	Control- Group 1: Standard diabetes care with x3 20 day periods of blinded Dexcom G6 CGM. 3-month study extension where converted to Tandem t:slim X2 with Control IQ technology and Dexcom CGM. Quality of life questionnaires completed at the end of this period and glucose data collected from the CGM. Intervention- Group 2: Tandem t:slim X2 with Control IQ technology and Dexcom G6 CGM + LCD
Participant Duration	9 months + 3 month optional study extension for standard care group

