Protocol Synopsis	
After consent eligibility will be assessed. The trial will consist of 3 phases:
 
Phase 1: Baseline data. All participants will complete 20 days of blinded CGM with Dexcom G6
 
Phase 2: Study Run in. Group 2 will have 2 weeks using the t:slim X2 pump with Control IQ technology and the Dexcom G6 CGM unblinded.
 
Phase 3: Study. 8 months. Group 1 will continue routine care as pre-study. They will undergo two periods of blinded Dexcom G6 CGM monitoring each lasting 20 days. Group 2 will continue on their allocated devices and LCD with close monitoring by the study team to ensure TIR is maximised. Both groups will undergo a hyperinsulinaemic hypoglycaemic clamp study at 0 and 8 months. Group 1 will be invited to take part in a 3 month study extension phase where they are converted to the study devices and complete quality of life questionnaires.

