## 2 STUDY OBJECTIVES

### 2.1 OBJECTIVES

#### 2.1.1 Primary Objective

Does maximizing TIR using AIDs with a LCD restore the glucagon response to insulin-induced hypoglycaemic in people with type 1 diabetes.

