## 2.2 ENDPOINTS

### 2.2.1 Primary Endpoint

The glucagon response to hypoglycaemia after a period of increased time in range using automated insulin delivery and a low carbohydrate diet compared with the glucagon response at baseline.

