#### Randomisation

We will perform stratified random sampling according to age, gender and BMI. We will then provide envelopes to randomly assign final members from the various strata,

these envelopes will be kept in a secure, locked unit within in the clinical research facility. This technique ensures that observations from all relevant strata are included in the sample. by stratified sampling to match for: age, gender and BMI. They will be assigned to one of two groups:

- Group 1: Controls: standard diabetes care with blinded CGM (Dexcom G6) on three occasions lasting 20 days. All will be invited to a 3-month study extension phase where they will be converted to the study devices.
- Group 2: New-generation AIDs (t:slim X2 insulin pump with Control-IQ technology) with CGM (Dexcom G6) and a low carbohydrate diet (30-40g of carbohydrate per main meal portion). They will also have a 20-day period of blinded CGM (Dexcom G6) at baseline

Amendment: 28/09/22: Recruitment and retention to group 1 has been challenging with potential participants not wanting to engage with the study if allocated to group 1. This has led to unbalanced study groups. Currently there are 11 participants in group 2 and only 3 participants in group 1 (with a further 2 participants previously recruited but choosing to leave the study early). In order to balance groups from now on participants will be approached to take part in the study and informed up-front that they will be allocated to group 1.

Dexcom G6 clinical supplies, technical and software assistance will all be provided by Dexcom (see letter of support: Dr [name], Senior US Medical Director, Dexcom).

Participants will be asked to choose an envelope at random at the end of the screening visit which will allocate them to a group. At this time arrangements for subsequent visits will be made. We will send those randomised to group 2 training materials for the insulin pump and CGM. Participants will be allocated to a group within 1 week of the screening visit. This will change in version 8 of the protocol (28/09/22), from this point participants will only be recruited to the control group (group 1) and not randomised.

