## 7 DATA COLLECTION

During the trial data will be collected by study staff. The following data will be collected at these time points:

1. Selection of potential participants prior to consent:
  - a. Review of electronic health care records, Trakcare and SCI Diabetes, for exclusion criteria
  - b. This data will be reviewed by study staff who are part of the participant's healthcare team
2. Eligibility Assessment (after obtaining written informed consent):
  - a. Inclusion and exclusion criteria assessment.
  - b. Demographics (date of birth, sex, race and ethnicity)

- c. Contact information (retained at the site and not entered into study database)
  - d. Medical history
  - e. Concomitant medications
  - f. Pregnancy test if applicable
  - g. HbA1c blood test
  - h. Bloods test for : Renal function and thyroid function
  - i. Urine sample for albumin:creatinine ratio
  - j. Physical examination to include: Weight, height, BMI, vital signs including measurement of blood pressure and heart rate
  - k. Modified gold score
  - l. Retinal screening will be arranged if this has not occurred in the previous 6 months
3. Baseline:
- a. CGM Data:
    - i. All participants will have blinded CGM data collected over a 20 day period (aiming to capture at least 14 days of data)
    - ii. This data will be collected automatically by the device after being fitted by the participant before being uploaded to a secure cloud-based platform
  - b. All participants will complete the study questionnaires:
    - i. Quality of life: EQ5D, Diabetes Specific Emotional Distress (DDS-1)
    - ii. Treatment satisfaction: Diabetes treatment satisfaction questionnaire
    - iii. Technology: Diabetes technology attitudes
    - iv. Fear of hypoglycaemia: Hypoglycaemia confidence, Fear of Hypoglycaemic Scale
  - c. All participants- first hypoglycaemic clamp study
4. Trial period
- a. Participants in group 2 will have data collected from their insulin pump and CGM device
  - b. Insulin pump data will be uploaded by the participant at least once per week to the secure platform Tandem t:connect
  - c. CGM data will be automatically uploaded to the secure cloud-based platform Dexcom Clarity
5. Midpoint
- a. Participants in group 1 will undergo a further 20 day period of blinded CGM data collection
  - b. All participants will have blood taken for HbA1c
6. Endpoint:
- a. Participants in group 1 will undergo a further 20 day period of blinded CGM data collection

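### The primary glucagon analysis is before/after within each group; no intervention-minus-control glucagon estimate is planned, although both groups have both clamps

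*Combined protocol and SAP*

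**What the plan says.** Section 9.2 sets the primary analysis: the glucagon response at the clamps is "compared to the individual's baseline glucagon responses within each group". The primary endpoint in 2.2.1 is the response after the intervention period "compared with the glucagon response at baseline". The two sections agree with each other.

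The design and the objective point elsewhere. The synopsis describes a "Randomised clinical feasibility trial with a 1:1 randomisation to Control IQ + LCD and routine care" and adds: "Both groups will undergo a hyperinsulinaemic hypoglycaemic clamp study at 0 and 8 months". Section 6.1 (Study Visit 7) repeats the second clamp for all participants. The primary objective in 2.1.1 asks: "Does maximizing TIR using AIDs with a LCD restore the glucagon response".

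Three other comparisons between participants are planned. In Section 9.2, "participants in the highest tertile of glycaemic TIR as a group over the 8 months will be compared" with those in the lowest tertile, as an exploratory analysis with no outcome named. Section 9.2 also compares time in range (TIR) in the Group 1 extension with TIR in Group 2. Section 2.2.2 compares TIR and quality of life between closed loop with the diet and closed loop alone.

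Section 6.1 (Randomisation) records that on 28/09/22 there were 11 participants in Group 2 and 3 in Group 1, with two more Group 1 participants having left early. From protocol version 8, new participants enter Group 1 only and are not randomised.

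**The concern.** The objective is a question about what the intervention does. A change from baseline in Group 2 mixes any effect of the intervention with everything else that can move a clamp result over eight months, such as assay or procedural drift, regression to the mean and the effect of being in a trial. A control group with the same two clamps exists to separate these. Under the plan as written, the control clamps are done but never enter an estimate of the difference.

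Readers would then set two before/after results side by side and take a significant change in one group and a non-significant change in the other as evidence of an effect. That pattern is not a test of the difference between the groups.

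**Working it through.** **1. Is a between-group glucagon estimate planned anywhere?**

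| Planned comparison | Where | Outcome | By allocated group? |
|---|---|---|---|
| Month 8 v own baseline | 2.2.1, 9.2 | Glucagon | No, within group |
| Highest v lowest TIR tertile | 9.2 | Not named | No, by TIR achieved after allocation |
| Group 1 extension v Group 2 | 9.2 | TIR | Yes, but not glucagon |
| Closed loop + diet v closed loop alone | 2.1.2, 2.2.2 | TIR, quality of life | Yes, but not glucagon |

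None is a Group 2 minus Group 1 glucagon estimate. Section 7 lists "All participants- first hypoglycaemic clamp study" under Baseline, so both groups have the first-clamp and month-8 results that such an estimate needs.

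**2. There is no figure in the plan to reproduce.** Section 9.1 rests the 24 participants on similarity to an earlier study and gives no alpha, power, SD or effect size. Section 9.2 states no test. Everything below is therefore illustrative.

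**3. Reading two within-group tests side by side.** Assume two-sided 5% paired t-tests and an identical true mean change in both groups, in units of the SD of change. If P2 and P1 are the noncentral-t powers in Groups 2 and 1, the chance of significance in Group 2 only is P2 × (1 − P1). At 11 v 13:

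| Shared shift (SD) | P2 (n = 11) | P1 (n = 13) | Group 2 only |
|---|---|---|---|
| 0 | 0.050 | 0.050 | 4.8% |
| 0.1 | 0.060 | 0.063 | 5.7% |
| 0.2 | 0.092 | 0.102 | 8.3% |
| 0.3 | 0.147 | 0.169 | 12.2% |
| 0.6 | 0.436 | 0.512 | 21.3% (peak) |

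At 12 v 12 the peak is 25.0%, at 0.62 SD.

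**4. Precision of the missing estimate.** The unadjusted 95% half-width in SD of change is t(0.975, n1 + n2 − 2) × √(1/n1 + 1/n2).

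- 11 v 13: 2.074 × 0.410 = 0.85. This assumes 24 participants excluding the two leavers, so 13 − 3 = 10 of 13 controls are non-randomised.
- 11 v 11: 2.086 × 0.426 = 0.89. This assumes the two leavers count towards 24 (24 − 11 − 3 − 2 = 8 more), so 8 of 11 controls are non-randomised.
- 11 v 3, randomised participants only: 2.179 × 0.651 = 1.42.

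**5. Choice of estimator when the groups may differ at clamp 1.** Suppose the groups differ by a stable amount at both clamps and nothing changes in either. The change-score difference is then centred on zero, while the clamp-1-adjusted (ANCOVA) estimate is centred on (1 − r) × the clamp-1 difference, where r is the correlation between clamps. With a 0.5 SD difference (SD of a single clamp response), that is 0.25 at r = 0.5 and 0.10 at r = 0.8. Simulated rejection rates at 11 v 13 (60,000 trials per cell, nominal 5%):

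| Clamp-1 difference | r | ANCOVA | Change score |
|---|---|---|---|
| 0.5 SD | 0.5 | 9.9% | 4.8% |
| 0.5 SD | 0.8 | 6.5% | 4.9% |
| 1 SD | 0.5 | 21.9% | 5.1% |
| 1 SD | 0.8 | 10.4% | 4.9% |

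With no clamp-1 difference, both methods reject in about 5%.

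**The case against.** The strongest reply is that this is a feasibility pilot (Section 3), that Section 9.2 is faithful to 2.2.1, and that a between-group estimate would be imprecise and, after version 8, mostly against non-randomised controls. All of that is true, and it bears on how serious the point is. It does not justify leaving the contrast out. Low precision argues for an interval rather than a test, a before/after result has no comparator at all, and recruiting more controls to balance the groups makes little sense unless the groups are compared.

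A second reply is that the objective concerns TIR, which the tertile contrast addresses. That is partly fair. But the contrast is exploratory, names no outcome, and sorts people by something achieved after allocation, so it cannot show what the intervention adds.

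Four stronger readings are tempting, and the documents do not support them:

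- That the plan carries a 25% false-positive rate. That figure is a peak at 12 v 12 and needs a shared shift of 0.62 SD. The documents give no expected shift, and 9.2 sets no decision rule. At small shifts the figure is close to 5%.
- That a between-group test would hold 5% whatever happens. It does so only if the groups are comparable, and controls recruited from version 8 are told their group in advance.
- That ANCOVA on everyone is plainly the right main analysis. Step 5 shows that it can mislead when the groups differ at clamp 1, and Group 2's first clamp follows up to two weeks on the study system.
- That the controls are fully concurrent and randomised. After version 8 this is only partly so.

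**Conclusion.** The gap is real: the primary analysis does not estimate the difference that the controlled design and the objective call for, and no other planned analysis supplies it. This finding rests on the text alone and needs no assumption.

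The size of the consequence does rest on assumptions (paired 5% tests, a common SD of change, and the final group sizes). At 11 v 13, a misleading pattern of significance in Group 2 only would occur in 4.8% to 12.2% of trials for shared shifts of 0 to 0.3 SD, and in 21% at worst. The missing estimate would have a half-width of 0.85 to 0.89 SD of change on the full set.

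This should be fixed, but it does not invalidate the trial. The study is a pilot, 9.2 matches its own endpoint, and rewording cannot turn a partly non-randomised comparison into a firm causal answer.

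**What to change.** In 9.2 and 2.2.1:

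1. Add the Group 2 minus Group 1 difference in glucagon response, with a 95% confidence interval, as the estimate that addresses the objective. Keep the within-group changes as descriptive.
2. Name in advance one glucagon summary measure, the same for both clamps. Section 6.1 has a pre-clamp sample and three draws at each of three plateaus, and the response is not otherwise defined.
3. Report the difference in change from clamp 1 and the ANCOVA estimate side by side, stating beforehand which leads. Say that they diverge if the groups differ at clamp 1: with a stable difference of 0.5 to 1 SD and no true change, ANCOVA at 11 v 13 rejects in about 7% to 22% of trials for correlations of 0.8 to 0.5, against about 5% for the change score.
4. Label the full-set estimate partly non-randomised and show the randomised-only estimate beside it.
5. Report by group the two early leavers, any data removed at a participant's request (Section 5.2.1) and any missing month-8 clamp.
6. State that Group 2's clamp 1 follows up to two weeks on the study system, so a comparison with it may miss an early effect.

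The cost is text only, with no new visits or samples. The price is candour about precision: the randomised-only half-width is about 1.42 SD at 11 v 3.

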### Monitoring Period

#### **Group 1**

Group 1 will continue on their standard diabetes care. At 4 months they will perform a 20 day period of blinded CGM monitoring. This will require them to insert the CGM device on two occasions during this 20 day period. During this 20 day period this group will continue on their standard diabetes care, including monitoring their own blood glucose, as they will not be able to view the data from the CGM device. Participants in this group will perform a further 20 day period of blinded CGM monitoring prior to the second hypoglycaemic clamp study. This means that participants in this group will have to insert the CGM device on 6 occasions during the study period. In each of these periods of blinded CGM monitoring the aim will be to collect at least 14 days of data. Study staff will collect the CGM devices at the end of each 20 day blinded period so that the data can be downloaded for analysis. CGM devices for these two blinded periods will be delivered to the participants' home. The device for the 4 month period will then be collected from the participant by study staff. The device used prior to the second clamp study can be given to study staff at the clamp study visit. During each of these blinded CGM periods participants will be asked to complete a 7-day food diary, to include 5 week days and 2 weekend days. This can be in the form of a paper diary provided by study staff or a mobile phone application. This can be returned to study staff at the next visit or by post, a stamped addressed envelope will be provided. After the second clamp study participants will be invited to take part in a 3-month study extension phase. During this time they will be converted to the study devices. They will be asked to upload their study pump once a week and will have ad hoc contact with the investigators over this time to adjust pump settings as required. At the end of the 3 months they will be sent quality of life questionnaires to complete along with a stamped addressed envelope to return these to the investigators.

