#### **Group 2**

Participants in group 2 will be continually monitored throughout the study period to ensure time in range is optimised throughout the 8 months. They will be asked to upload their insulin pump data at least once weekly to the online platform Tandem t:connect. This is done using a USB device provided with the insulin pump and the participants own computer or laptop with internet access. Participants will be given training in the use of the platform and account logins as part of their pump training. The data from the participant's CGM device will also be reviewed by study staff. This data automatically uploads to the Dexcom Clarity cloud platform without the need for the participant to physically attach the device to their computer. Study staff will review blood glucose data on Dexcom clarity daily to ensure time in range is being maximised.

Study staff will review the uploaded pump data at least once weekly using administrative log-in details and will contact participants by telephone if the data suggests:

1. Adjustments are required to insulin pump settings (carbohydrate ratios, insulin sensitivity factor, basal rates) as they are experiencing time out of the target glycaemic range
2. The participant is not changing the insulin pump set every 3 days
3. The participant requires further education about the low carbohydrate diet or carbohydrate counting

4. The participant is experiencing multiple alarms or error codes

Participants will have contact information for study staff and will be able to contact staff via email or telephone on an ad hoc basis throughout the study.

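### The tertile contrast and the extension comparison in Section 9.2 would be stronger with continuous time in range and matched CGM windows, and the extension comparison does not isolate a diet effect

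*Combined protocol and SAP*

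**What the plan says.** Section 9.2 makes the primary analysis a comparison of the glucagon response with each person's own baseline, within each group. It then adds exploratory analyses in which "the participants in the highest tertile of glycaemic TIR as a group over the 8 months" are compared with those in the lowest tertile. That sentence does not repeat the outcome, give a model, or say which CGM days define TIR.

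Section 6.1 (Monitoring Period) gives the CGM schedule after the first clamp. For Group 1: "At 4 months they will perform a 20 day period of blinded CGM monitoring", and "Participants in this group will perform a further 20 day period of blinded CGM monitoring prior to the second hypoglycaemic clamp study". Group 2 wears unblinded CGM throughout the 8 months.

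Section 9.2 also states: "The TIR of participants completing the study 3-month extensions will be compared to that of group 2 during the study". Sections 2.1.2 and 2.2.2 give this contrast its purpose, which is closed loop with the low carbohydrate diet against closed loop without it, for TIR and quality of life. In the extension, participants "will have ad hoc contact with the investigators over this time to adjust pump settings as required". In Group 2, "Study staff will review blood glucose data on Dexcom clarity daily to ensure time in range is being maximised". The extension is optional and follows the second clamp. Under Randomisation, the version 8 amendment says that "from this point participants will only be recruited to the control group (group 1) and not randomised".

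**The concern.** (a) Cutting TIR into thirds and comparing the extremes discards a third of a sample of 24. It also ranks people on a TIR measured over different days, and under different blinding, in the two groups. Because the intervention is meant to raise TIR, a pooled tertile partly encodes group. A top-versus-bottom difference could therefore be reported as a TIR-glucagon link separate from allocation when the analysis cannot show that.

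(b) The extension comparison is the planned TIR analysis for a stated secondary objective and endpoint about diet. Several things other than diet differ between its two sides, and Section 9.2 carries no caution. A difference in TIR or quality of life could be credited to the diet when closer oversight, longer use or self-selection explains it.

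**Working it through.** The plan gives no figure to reproduce here. Section 9.1 states no effect size, SD, alpha or power.

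**(a) Tertiles**

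Inputs from the documents: 24 participants, 1:1 (12 v 12). TIR is 59±14 for control and 71±12 for closed loop (Section 1.1, closed-loop trial results). No TIR is given for closed loop plus diet, so Group 2 is shown at 65±12, 71±12 and 80±10; the first and last are assumptions. Also assumed: two-sided 5% tests and a pooled TIR-glucagon correlation of 0.5.

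- Tertile size if pooled: 24/3 = 8, so 8 v 8 with 8 dropped.
- CGM coverage in Group 1: 2 × 20 = 40 days of about 243, which is 40/243 = 16%. Group 2's CGM is continuous.
- Model for power: glucagon = r·z + √(1 − r²)·e, where z is TIR standardised over both groups, r = 0.5 and e is standard normal. There is no clamp-1 term. Values are simulated, good to about one percentage point.

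| Group 2 TIR | Top tertile in Group 2 | Bottom tertile in Group 1 | Power: pooled tertiles | Power: continuous TIR | Power: TIR + group |
|---|---|---|---|---|---|
| 65±12 | 61% | 64% | 58% | 73% | 69% |
| 71±12 | 72% | 76% | 58% | 73% | 63% |
| 80±10 | 87% | 93% | 60% | 74% | 49% |

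Continuous TIR gains about 15 points over tertiles. Adding group then costs 4, 10 and 25 points. The reason is collinearity. With d the difference in mean TIR, the share of TIR variance explained by group is (d/2)² / [(s₁² + s₂²)/2 + (d/2)²]:

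- 65±12: 9/(170 + 9) = 0.05
- 71±12: 36/(170 + 36) = 0.17
- 80±10: 110.25/(148 + 110.25) = 0.43

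The large-sample variance inflation of the TIR slope, 1/(1 − share), is 1.05, 1.21 and 1.74.

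If tertiles were instead cut within each group and combined with a group term, power would be about 52, 48 and 35%.

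False signal: suppose TIR has no effect and group has an assumed 1 SD effect on glucagon by another route. Pooled tertiles then reject in about 7, 14 and 30% of trials. Continuous TIR without group does much the same (about 7, 14 and 30%). TIR with group rejects in 5%. At an assumed 0.5 SD, pooled tertiles give about 6, 7 and 12%.

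**(b) Extension v Group 2**

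| | Extension | Group 2 |
|---|---|---|
| Time on devices | 3 months | 8 months |
| Oversight | ad hoc contact | daily CGM review, prompted calls |
| Who is analysed | opted in and completed | allocated at entry |
| Order | after about 8 months of routine care | at study start |
| Quality-of-life questionnaires | after 3 months on devices | at month 8 |

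Weekly pump upload is common to both.

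Allocation: the amendment reports "Currently there are 11 participants in group 2 and only 3 participants in group 1", plus 2 who left Group 1 early. Assume enrolment reaches 24, all later entrants join Group 1 and nobody else leaves. Counting the leavers, 24 − 16 = 8 more, so 8/11 = 73% of Group 1 is non-randomised. Not counting them, 24 − 14 = 10 more, so 10/13 = 77%.

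Precision: the 95% half-width is t × 12 × √(1/n + 1/11), with an assumed SD of 12 and n in the extension against 11.

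- n = 3: 2.179 × 12 × 0.651 = 17.0 points
- n = 6: 2.131 × 12 × 0.507 = 13.0
- n = 9: 2.101 × 12 × 0.449 = 11.3
- n = 11: 2.086 × 12 × 0.426 = 10.7

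Adjusting for a prior blinded window correlated 0.5 (assumed) with later TIR multiplies these by √0.75 and uses one fewer degree of freedom: 14.9, 11.3, 9.9 and 9.3.

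**The case against.** Much of the case for leaving the plan alone is fair.

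- A reader might infer that the plan leaves the pooling question wide open. It hardly does. The primary analysis is explicitly within group, the tertile sentence drops that qualifier, and the paragraph is about glucagon. Pooled, with glucagon as outcome, is the natural reading.
- A reader might infer that within-group tertiles would be nearly useless, at about 20% power. That figure is 4 v 4 in Group 2 alone. Combined across groups the power is 52, 48 and 35%, and the false-signal rate is 5%.
- A reader might infer that pooled tertiles will produce false TIR findings. The documents do not support this. It needs a group effect on glucagon that bypasses TIR, and no passage gives one of any size. The protocol's hypothesis runs through TIR, so the between-group TIR difference is the intended exposure.
- Continuous TIR is not better in every respect. Without group it has the same confounding as tertiles. With group it can have less power than pooled tertiles when the groups separate widely, which is what the trial tries to achieve.
- The plan says only that extension TIR will be compared with Group 2. It does not claim a causal diet effect, and re-cutting the windows leaves the comparison confounded.

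What stands: the discarded middle third, the unequal CGM windows, and a comparison framed by diet in Sections 2.1.2 and 2.2.2 that carries several other differences without a caution.

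**Conclusion.** The point holds as an inexpensive improvement. The primary analysis is not affected, the tertile contrast is labelled exploratory, and this is a feasibility pilot.

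For (a), continuous TIR adds about 15 points of power over pooled tertiles at an assumed correlation of 0.5. Including group separates TIR from allocation, at a cost of 4 to 25 points over the TIR range shown. Neither slope suffices alone, so both are needed. The power figures rest on the assumed correlation and Group 2 TIR. The false-signal figures rest on the further assumption of a non-TIR group effect and illustrate a risk only. The benefit of matched windows is comparability; no bias from the unequal windows has been quantified.

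Part (b) carries more weight because it serves a secondary endpoint. The differences in duration, oversight, selection, order and allocation are stated in the protocol and rest on no assumption. The comparison is also imprecise, at about ±11 to ±17 TIR points unadjusted, and the documents give no diet effect on TIR to set against that.

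**What to change.** **(a)** Replace the tertile contrast with a regression in all participants of the month-8 glucagon response on continuous TIR, adjusted for the clamp-1 response. This keeps the outcome relative to baseline, as Sections 2.2.1 and 9.2 define it. Note that Group 2's clamp 1 follows up to 2 weeks on the devices, with diet advice already given, so it is not a clean pre-treatment value.

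Compute TIR in both groups from the same two windows, 20 days at month 4 and 20 days before clamp 2. Give Group 2's full 8-month TIR as a supportive summary. Report the TIR slope with a 95% CI both without and with group. State in advance that the slope without group cannot be separated from allocation. State also that, with group in the model, a wide interval or loss of significance is not evidence of no link.

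**(b)** Compare TIR over the 3 months from device start in everyone who starts the extension with Group 2's first 3 months from device start, run-in included. Adjust for each person's last blinded CGM window before device start: the one before clamp 2 in Group 1, and Visit 2 in Group 2. Report the difference with a 95% CI. State that this comparison and the quality-of-life one (3 v 8 months on devices) are descriptive and do not isolate a diet effect. Name oversight, self-selection, order and non-randomised entry as alternative explanations.

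**Cost:** wording in Section 9.2 and re-cutting of CGM data the protocol already collects, with no new visits or samples. The matched windows leave about 84% of Group 2's record out of the main model. The blinded-versus-unblinded difference remains. The oversight and selection differences in (b) cannot be removed, and the quality-of-life timing cannot be matched with the scheduled questionnaires.
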